7.4.3. Other Multiplicity Adjusted Secondary Efficacy Variable and Analysis

For continuous endpoints such as change from Baseline using observed data only, the main estimand will be similar to the non-EMA-Estimand for the primary endpoint, analyzed using the mITT population with treatment policy strategy to handle ICEs. An MMRM model as described in Section 7.2 for the primary endpoint will be used with Baseline value of the analyzed variable replacing Baseline UHDRS-TFC as a covariate. For the specified visits, the LSMs, SE of the estimates, p-values, and 2-sided 95% CIs will be provided for the within treatment group changes from Baseline and for the comparison of change from Baseline between pridopidine and placebo.

Supportive estimands for continuous endpoints will be similar to the EMA-Estimand for the primary endpoint, with population as the ITT population and missing values imputed using copy reference method under MNAR assumption. Additional missing value imputation approach under MAR assumption may be used as a sensitivity analysis.

For analysis of change from Baseline in UHDRS-TFC at Week 78, main analysis will include observed values at scheduled visits up to 78 weeks. A sensitivity analysis for Week 78 endpoints will be performed with assessments between Week 65 and 78 mapped to Week 78.

For positive response defined using values of continuous variables:

- Unless otherwise specified, where a decrease reflects disease progression, a responder will be defined as those with no change or improvement (change from Baseline ≥ 0)
- Unless otherwise specified, where an increase in score reflects disease progression, a responder will be defined as those with change from Baseline ≤ 0

Main estimands for binary endpoints will be similar to the main estimand for the binary UHDRS-TFC response, analyzed in the mITT population and with ICEs handled by a combined composite and hypothetical strategy. Supportive estimand for the binary endpoints will be similar to Supportive Estimand 1 for the binary UHDRS-TFC response. All responder analyses or analyses of binary variables will be performed using logistic regression as indicated for the binary secondary variable above in Section 7.4.1.

The p-values from the main estimand will be used in the hierarchical testing for multiplicity adjusted secondary endpoints following the order described in Section 3.2.2.

Subgroup analyses as described in Section 7.3.2 for the primary efficacy endpoint will also be performed for the multiplicity adjusted secondary endpoints and log2-transformed NfL.

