After signing informed consent, participants will undergo screening assessments to determine eligibility over a Screening period of up to 6 weeks⁶.

The Screening period will be followed by a 65- to 78-week double-blind Treatment period, composed of a 2-week Titration period, a 63-week double-blind full-dose Maintenance Treatment period followed by a variable double-blind Treatment period of up to 13 weeks (total of up to 78 weeks; Main Study).

On Day 1 (Baseline visit), eligible participants will be randomized in a 1:1 ratio to active (pridopidine 45 mg bid) or control (placebo) arm as shown in [Table 1](#). Randomization will be stratified by Baseline HD stage (HD1 vs. HD2) and baseline Neuroleptic use (Yes/No).

Starting on Day 1, during the Titration period, all participants will self-administer 1 capsule of study drug orally (PO), once daily (QD), in the morning for 2 weeks. Thereafter, the study drug will be taken PO bid in the morning and in the afternoon (7-10 hours apart) for 63 weeks (double-blind full-dose Maintenance Treatment period). Participants who complete the Maintenance period (63 weeks) will continue into a variable double-blind period of up to 13

⁶ If there is no need for genetic tests or washout from prohibited medication, the screening period should be completed within 3 weeks.

weeks or until the last participant randomized completes 65 weeks of treatment (2-weeks Titration + 63-weeks full-dose), whichever comes first. Most participants will be followed for 78 weeks. Participants entering the study within 90 days of the last randomized participant will be followed between 65 and 78 weeks. As soon as the last participant reaches Week 65, the Main study EoS visit for all remaining participants who are between Week 65 and Week 78 needs to be conducted within 4 weeks.

For participants who complete their Week 65 visit within 4 weeks of the last participant completing Week 65, the Week 65 visit will be considered the EoS Visit. For participants who are beyond 4 weeks from their Week 65 visit when the last participant reaches Week 65, and have not had a Week 78 visit, the EoS visit will be conducted within 4 weeks.

The double-blinding will be maintained for all participants and Investigators until that time.

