3.2.2. Multiplicity-adjusted Secondary Efficacy Endpoints

The key secondary efficacy endpoint for this study is:

- change from Baseline to Week 65 in cUHDRS total score

The other multiplicity-adjusted secondary efficacy endpoints for this study are to evaluate the efficacy of pridopidine 45 mg bid vs. placebo as measured by:

- the proportion of participants with improvement or no worsening in UHDRS-TFC at Week 65 (change from Baseline \geq 0 points) using responder analysis
- change from Baseline to Week 52 in UHDRS-TFC score
- change from Baseline to Week 78 in UHDRS-TFC score
- change from Baseline to Week 65 in Q-Motor [REDACTED]
[REDACTED]

- change from Baseline to Week 65 in UHDRS-TMS (defined as the sum of all UHDRS motor domains ratings)
- change from Baseline to Week 65 in SDMT score
- change from Baseline to Week 52 in UHDRS-TMS score
- proportion of participants with no change or improvement in CGI-C at Week 65

For responder analyses where there are fewer than 5 responders (overall between both treatment groups), the analyses will not be performed as too few responders will not allow for comparison of responders between treated and placebo participants.

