- Under the assumptions of MAR that missingness depends on the observed values and can be predicted based on a participant's observed data, the missing value will be imputed using monotone regression model. The imputation model will include Baseline and all post-baseline values for the efficacy endpoint to be imputed, treatment, randomization strata, and region. Multiple imputations will be performed to assign the response variable at consecutive study visits in a sequential manner for the monotone missing data pattern.
- Under the assumptions of MNAR that missingness depends on unobserved values and cannot be predicted solely based on a participant's observed data, the missing value will be imputed using a pattern-mixture model (PMM). In the PMM, the distribution of a response is modeled as the mixture of a distribution of the observed responses and a distribution of the missing responses. As the missing values for participants in the pridopidine group may imply these participants no longer receive the treatment, it is then reasonable to assume that the conditional distribution of the missing values, given observed data, is similar to that in the placebo group, and impute the missing values in pridopidine group based on the conditional distribution from the placebo group.

This will be realized by PMM with control-based pattern imputation, a variant of the copy reference method (Little and Wang, 1996; Ratitch and O'Kelly, 2013). In this imputation approach, the model for missing observations is constructed from the observed data in the placebo group only, and then used as the imputation model for missing values in pridopidine and placebo groups. Following the chain-based imputations, multiply imputed datasets will be analyzed using the same MMRM as for primary analysis (Section 7.2).

At the last step, the estimates from all imputed datasets will be combined using Rubin's rule for an overall inference. SAS Procedures, MI, MIXED and MIANALYZE will be used for above steps.

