3. Compound symmetry with heterogeneous variances (CSH),
4. Toeplitz (TOEP),
5. Autoregressive (1) [AR(1)], and
6. Compound Symmetry (CS).

Denominator degrees of freedom for the F-test for fixed effects will be estimated using the Kenward-Roger approximation. The least square mean (LSM) and standard error (SE) of the LSM for each treatment group, the 95% CI and p-value for the comparisons (change from Baseline in pridopidine 45 mg bid vs. placebo) will be presented at Week 65.

For EMA regions, the main estimand is defined as **EMA-Estimand**:

- Treatment: Pridopidine 45 mg bid or placebo (on background of standard of care) that participants are randomized to
- Population: Early HD Participants (HDI & HD2) defined through the study inclusion/exclusion criteria. The ITT population will be used in analyzing this estimand
- Variable: Change from Baseline to Week 65 in UHDRS-TFC
- Population Level Summary: LS-Mean difference between pridopidine 45 mg bid and placebo from MMRM model in change of UHDRS-TFC from Baseline to Week 65
- ICEs and Strategies for Addressing ICEs:

ICEs include treatment discontinuation or death and will be handled by a composite of treatment policy and hypothetical strategies.

- Treatment policy strategy will apply to all observed values including those collected after treatment discontinuation as these values reflect the remaining off-drug treatment effect in reality.
- Hypothetical strategy will apply to missing values after the last observed values. The method of MI will be applied to impute the missing data using PMM with control-based pattern imputation under MNAR assumptions (details in Section 5.8.1).

Since UHDRS-TFC is used as a continuous variable in the MI procedure, the imputed values will take continuous values instead of the discrete values ranging from 0 to 13. To avoid the influence of extreme values outside the range, the continuous values will be categorized to 0 if the imputed values < 0.5 , and to 13 if the imputed values ≥ 12.5 . All the other values in $[0.5, 12.5)$ will be rounded to the nearest integer between 1 and 12.

The MI method uses SAS PROC MI and MIANALYZE to generate multiple complete datasets and combine the model results from them as described in Section 5.8.1. The LSM and associated SE for each treatment group, the 95% CI and p-value for the comparisons (pridopidine 45 mg bid vs. placebo) will be presented at Week 65.

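### The supportive copy-reference analysis of UHDRS-TFC at Week 78 does not exempt participants still on study drug whose Main Study ended before Week 78 by design

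*SAP*

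**What the plan says.** SAP 3.2.2 lists "change from Baseline to Week 78 in UHDRS-TFC score" among the multiplicity-adjusted secondaries; it is fourth in the order of SAP Section 2. For this group SAP 7.4.3 states: "Supportive estimands for continuous endpoints will be similar to the EMA-Estimand for the primary endpoint". It specifies the ITT population and "missing values imputed using copy reference method under MNAR assumption".

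The EMA-Estimand in SAP 7.2 sets the scope: "Hypothetical strategy will apply to missing values after the last observed values". Its intercurrent events are limited: "ICEs include treatment discontinuation or death and will be handled by a composite of treatment policy and hypothetical strategies". Administrative end of the Main Study is not named. SAP 5.8.1.2 builds the imputation model from placebo data alone, on the ground that "missing values for participants in the pridopidine group may imply these participants no longer receive the treatment".

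The design leaves some participants short of Week 78. Protocol 1.1 states: "Participants entering the study within 90 days of the last randomized participant will be followed between 65 and 78 weeks". Protocol 1.1 and SAP 3.1 make Week 65 the end-of-study visit for those whose Week 65 visit falls within 4 weeks of the last participant's.

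SAP 7.4.3 makes three other provisions that bear on Week 78:
- a main analysis of observed values;
- a separate sensitivity analysis that maps assessments between Weeks 65 and 78 to Week 78;
- an optional MAR imputation.

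**The concern.** Copy reference is a reasonable assumption for someone who has stopped drug. A late entrant who attends the last Main Study visit on study drug has not stopped. The Week 78 value is absent because the calendar ran out, yet the rule as written treats it like a value lost to discontinuation.

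The SAP separates missing data by reason elsewhere. Intermittent gaps are imputed under MAR (5.8.1.2), COVID-19 gaps are handled under MAR (7.1.1), and the binary TFC response splits discontinuations by cause (7.4.2). The silence on administrative end at Week 78 looks like an oversight.

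What is at stake is interpretation. Week 78 was moved up the hierarchy to show durability within the double-blind period. If the supportive estimate falls below the main one, the gap would naturally be read as sensitivity to dropout, when part of it would reflect enrolment dates.

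**Working it through.** **The plan's own figures (Week 65 only; there is none for Week 78).** Power = Φ(δ / (σ√(2/n)) − 1.96), with n per arm.
- n = 186, δ = 0.7, σ = 1.9: 0.7/0.197 = 3.55, power 0.944 (plan: 94%).
- 372/0.775 = 480.
- 0.7 × 0.775 + 0.1 × 0.225 = 0.565. With n = 240: 0.565/0.1735 = 3.26, power 0.90 (plan: 90%).

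These reproduce.

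**How many are affected.** Inputs: 499 randomized (SAP version history); recruitment Q3 2020 to about Q4 2021 (Protocol 4.4), taken as 366 to 548 days. Uniform accrual is an assumption.

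| Entry before the last participant | Meaning | Share | Number of 499 |
|---|---|---|---|
| 28 days | Week 65 is end of study (Protocol 1.1, SAP 3.1) | 28/548 to 28/366 = 5-8% | 25-38 |
| 63 days | cannot reach Week 78 in the 4-week allowance (13 − 4 = 9 weeks) | 11-17% | 57-86 |
| 90 days | followed 65 to 78 weeks | 16-25% | 82-123 |

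With the ±14-day visit window, the second row shrinks to 7 weeks: 49/548 to 49/366, or 9-13%.

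**How far the estimate moves.** For an affected pridopidine participant, the imputed Week 78 difference is Σ bₖδₖ. Here bₖ are the placebo regression coefficients of Week 78 on Weeks 26, 39, 52 and 65, and δₖ are the treatment differences at those visits. The placebo arm is not distorted. With affected share a, and leaving other dropout aside:

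overall = (1 − a) × δ₇₈ + a × Σ bₖδₖ

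The plan supplies δ₆₅ = 0.7 and SD 1.9. The effect profile and the correlations are assumptions: compound symmetry with ρ 0.5 and 0.7, AR(1) with ρ 0.7 and 0.85, and a random slope carrying 50% or 80% of the Week 65 variance.

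Example: linear growth gives δ = 0.28, 0.42, 0.56, 0.70 (sum 1.96) and δ₇₈ = 0.7 × 78/65 = 0.84. With compound symmetry at ρ = 0.5, each b = 0.5/(1 + 3 × 0.5) = 0.2, so the imputed difference is 0.2 × 1.96 = 0.392. At a = 25% the overall difference is 0.75 × 0.84 + 0.25 × 0.392 = 0.728.

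Ranges over the six covariances:

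| Effect profile | δ₇₈ | Imputed | a = 5% | 11% | 17% | 25% |
|---|---|---|---|---|---|---|
| Linear growth | 0.84 | 0.39-0.75 | 0.82-0.84 | 0.79-0.83 | 0.76-0.83 | 0.73-0.82 |
| Linear to Week 65, then flat | 0.70 | 0.39-0.75 | 0.68-0.70 | 0.67-0.71 | 0.65-0.71 | 0.62-0.71 |
| Constant | 0.70 | 0.49-0.98 | 0.69-0.71 | 0.68-0.73 | 0.66-0.75 | 0.65-0.77 |

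**The case against.** The strongest reply is that nothing confirmatory depends on this. SAP 7.4.3 takes the hierarchical p-values from the main estimand, an observed-data MMRM valid under MAR, and MAR suits administrative missingness. This stands in full.

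A second reply is that the text never prescribes copy reference for administrative end. SAP 5.8.1.2 introduces monotone missingness through participants who discontinue, Protocol 9.4.2 speaks of trajectories after discontinuation, and the supportive estimand is only similar to the EMA one. That leaves room for a sensible programmer. But these participants' data are also monotone, the scope clause in 7.2 covers every value after the last observed one, and nothing exempts them. Followed literally, the rule includes them.

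A third reply is that other Week 78 analyses bracket the result. The mapping analysis is separate and cannot help anyone with nothing after Week 65. The SAP does not say whether mapping also applies within the copy-reference analysis. The Week 78 per-protocol set drops these participants, and MAR imputation is optional.

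Some stronger readings are tempting, and the documents do not support them:
- *These participants receive a whole placebo trajectory.* The model conditions on their own values through the last visit, so only about 13 weeks borrow from placebo.
- *Most imputed Week 78 values are administrative.* Planned dropout is 22.5%, or 112 of 499, which only the top of the 82-123 range exceeds. SAP 3.6.3.1 calls discontinuation low but gives no rate.
- *All late entrants are on drug.* SAP 5.5.7 counts Week 65 completers whether on or off treatment, and Protocol 7.2 encourages those off drug to stay.

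**Conclusion.** The point holds as a defect in one supportive analysis. The rule places an off-treatment assumption on participants who may be on treatment at their last visit, and no other provision removes it.

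The size is modest. With linear growth the supportive difference falls from 0.84 to about 0.73-0.83 at shares of 11-25%, and to no less than 0.82 at 5%. With a plateau or a constant effect it usually falls, but under some correlation structures it rises slightly, so a uniform bias toward zero should not be claimed. Accrual pattern, Week 78 effect and covariance are all assumed.

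A reader might apply the plan's 0.1-point allowance to these participants as well. At a 25% share of the planned 77.5% completers, 0.7 × 0.581 + 0.1 × 0.419 = 0.449, with power of 73%. That overstates the loss, because these participants have on-study data through Week 65 and no hierarchical test uses this analysis. Type I error and the confirmatory Week 78 test are unaffected.

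**What to change.** Add to SAP 7.4.3, for the Week 78 supportive analysis:
- Impute values missing only because the Main Study ended, in participants still on study drug at their last Main Study visit, under MAR within randomized arm.
- Keep copy reference for values missing after study drug discontinuation, study withdrawal or death.
- Report the number in each category by arm, and state whether the mapping of Week 65 to 78 assessments applies in this analysis.

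The condition on drug status matters. Restricting copy reference to study withdrawals alone would give own-arm imputation to participants who stopped drug but stayed in the study, against the SAP's own rationale.

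The flag also needs one definition of administrative end. Protocol 4.1 makes Week 65 the end-of-study visit for everyone who cannot reach Week 78 within the 4 weeks. Protocol 1.1 and SAP 3.1 give those more than 4 weeks past Week 65 a later visit. Under uniform accrual, the share with nothing after Week 65 is 11-17% on one reading and 5-8% on the other. These passages must be reconciled.

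The cost is a few lines of text and one flag from disposition and dosing data. The supportive analysis becomes slightly less conservative.

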3.3. Sample Size and Power Considerations

Based on experience with early HD participants in the prior Phase 2 PRIDE-HD study, we expect the difference in mean change from Baseline to Week 65 between the 45 mg bid treated and placebo groups to be 0.7 points on the UHDRS-TFC with a standard deviation (SD) of 1.9 points.

A total sample size of 372 participants will provide 94% power to detect a between-group difference of 0.7 points in the mean change from Baseline to 65 weeks in the UHDRS-TFC score, with an SD of 1.9 points, using a two-tailed t-test at a significance level of 0.05. Assuming a drop-out rate of 22.5%, a total of 480 participants will be randomized. The sample size was calculated using SAS version 9.4 PROC POWER.

Based on feedback from Regulatory Authorities, the power assessment was updated as below. Assuming a dropout rate of 22.5 % in each treatment group early in the study, under assumption of Missing Not at Random (MNAR) with imputed values for all discontinued participants estimated based on the trajectory of placebo participants with available data, we anticipate a difference in change from Baseline to imputed values at Week 65 for this group to be 0.1 points. The overall difference would then be 0.565 (0.7*0.775+0.1*0.225) or 0.7 points for the 77.5% completers and 0.1 points for the 22.5 % participants who discontinue and have imputed data at Week 65. A difference of 0.565 points with SD of 1.9 with a sample size of 480 participants would provide 90% power (SAS V 9.4 PROC POWER).

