7.4.2. UHDRS-TFC Response as a Binary Endpoint

The binary UHDRS-TFC response (yes or no) is defined as achieving improvement or no worsening in UHDRS-TFC score, i.e., change from Baseline to Week 65 in UHDRS-TFC ≥ 0

points. The responder analysis will be performed for the proportion of participants with change from baseline to Week 65 in UHDRS-TFC ≥ 0 .

The hypothesis testing to compare the percentage of responders between the two treatment groups will be based upon the mITT population. Logistic regression will be used to analyze and compare the probability of whether a participant is a UHDRS-TFC responder or not. The model will adjust for Baseline UHDRS-TFC, region, Baseline randomization stratification factors of neuroleptic use (Yes/No) and HD stage (HD1 and HD2).

The hypothesis testing of the UHDRS-TFC responder analysis is based on the main estimand as follows:

- Treatment: Pridopidine 45 mg bid or placebo (on background of standard of care) that participants are randomized to
- Population: Early HD Participants (HD1 & HD2) defined through the study inclusion/exclusion criteria. The mITT population will be used in analyzing this estimand
- Variable: Improvement or no worsening (change from Baseline ≥ 0 points) at Week 65 in UHDRS-TFC (Defined as responders to treatment)
- Population Level Summary: Proportion of responders, defined as the proportion of participants achieving improvement or no worsening in UHDRS-TFC (change from Baseline ≥ 0 points) at Week 65
- ICEs and Strategies for Addressing ICEs:

ICEs include treatment discontinuation and will be handled by combining composite strategy and hypothetical strategy as follows:

- Composite strategy: Observed UHDRS-TFC values will be used to determine if a participant is a responder or not. For treatment discontinuation due to disease-progression-related death, or meeting Stopping Rules, the participant will be considered a non-responder.
- Hypothetical strategy: For treatment discontinuation due to other reasons not included in composite strategy and no TFC data collected afterward, all values after ICEs will be imputed under MAR as if the participants had continued receiving the study treatment. The MAR imputation model will include UHDRS-TFC as a continuous response variable as described in Section 7.2. The UHDRS-TFC response at Week 65 (change from Baseline in UHDRS-TFC ≥ 0) will then be derived using the imputed UHDRS-TFC score as well as the non-missing UHDRS-TFC scores.

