7.5. Non-Multiplicity Adjusted Secondary Efficacy Variable and Analysis

Other non-multiplicity adjusted secondary efficacy variables are listed and defined in Sections 2 and 3.2.3.

For all Q-Motor analyses [REDACTED]

[REDACTED] Analysis of Q-Motor [REDACTED]

For continuous variables, an MMRM model as described in Section 7.2 for the primary endpoint in mITT population will be used, with Baseline value of the analyzed variable replacing Baseline UHDRS-TFC as a covariate. For the specified visits, the LSMs, SE of the estimates, p-values, and 2-sided 95% CIs will be provided for the within treatment group changes from Baseline and for the comparison of change from Baseline between pridopidine and placebo. This will be repeated in W65PP or W78PP population depending on whether change to Week 65 or 78 is analyzed.

In addition, actual values and changes from Baseline to each visit will be summarized using descriptive statistics for each endpoint. The sub-scale scores of each endpoint will also be summarized where applicable.

The proportion of responders will be analyzed in a similar way to how the binary UHDRS-TFC response is analyzed for the main estimand and Supportive Estimand 1. Different thresholds than specified above may be explored. Descriptive statistics and 95% CI using normal approximation will be provided for the proportions at each visit. In order to minimize impact of outliers that may represent unrealistic changes in key endpoints, analyses using robust regression or other methods may be performed.

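### Read literally, the UHDRS-TMS and cUHDRS responder models adjust for Baseline UHDRS-TFC rather than the endpoint's own Baseline, at a modest cost in power

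*SAP*

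**What the plan says.** The logistic model is set out for UHDRS-TFC response in SAP 7.4.2: "The model will adjust for Baseline UHDRS-TFC, region, Baseline randomization stratification factors", the stratification factors being neuroleptic use and HD stage. SAP 7.4.3 extends it: "All responder analyses or analyses of binary variables will be performed using logistic regression as indicated for the binary secondary variable above". That sentence points to Section 7.4.1, which is the cUHDRS repeated-measures section and contains no logistic model.

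The UHDRS-TMS, cUHDRS and Q-Motor responder endpoints are defined in SAP 3.2.3 as non-multiplicity-adjusted, so SAP 7.5 governs them: "The proportion of responders will be analyzed in a similar way to how the binary UHDRS-TFC response is analyzed". Protocol 9.4.3 likewise says only that such endpoints are handled like UHDRS-TFC response, and it lists no covariates.

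For continuous endpoints the SAP is explicit. Section 7.4.3 fits the primary model "with Baseline value of the analyzed variable replacing Baseline UHDRS-TFC as a covariate", and 7.5 repeats this. The NfL responder model in SAP 9.1.2, objective (4), names Baseline log2(NfL).

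**The concern.** For UHDRS-TFC response, Baseline UHDRS-TFC is the endpoint's own Baseline. Carried over unchanged to UHDRS-TMS or cUHDRS response, it is a different variable from the one whose change defines response. Whether a change crosses a threshold depends on the score's own starting value, through regression to the mean. Leaving that value out can cost power. A chance imbalance in it is then corrected only as far as Baseline UHDRS-TFC and HD stage track it. The continuous model of the same score does correct for it, so part of any gap between the two results could come from the covariate alone.

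**Working it through.** **Step 1: which Baseline each model names.**

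| Model | Place | Baseline covariate |
|---|---|---|
| UHDRS-TFC response | SAP 7.4.2 | UHDRS-TFC (own) |
| Continuous UHDRS-TMS, cUHDRS, Q-Motor | SAP 7.4.3, 7.5 | own, stated |
| NfL response | SAP 9.1.2 (4) | own, stated |
| UHDRS-TMS and cUHDRS response | SAP 7.5 via 7.4.2 | no change stated, so UHDRS-TFC |
| Q-Motor response | SAP 7.5 via 7.4.2 | same, but nearby text is redacted |

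**Step 2: the plan's own power figures.** These concern the primary endpoint only. SAP 3.3 states: "A total sample size of 372 participants will provide 94% power to detect a between-group difference of 0.7 points", "using a two-tailed t-test at a significance level of 0.05", with SD 1.9. Using power = Φ(δ / (σ√(2/n)) − 1.96):
- δ = 0.7, n = 186 per arm: 0.7 / (1.9 × √(2/186)) = 3.553, so Φ(1.593) = 94.4%.
- δ = 0.7 × 0.775 + 0.1 × 0.225 = 0.565, n = 240 per arm: 0.565 / (1.9 × √(2/240)) = 3.257, so Φ(1.297) = 90.3%.
- 372 / (1 − 0.225) = 480.

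All reproduce. The SAP gives no power, responder rate or Baseline correlation for the responder endpoints at issue, so the next steps rest on assumptions.

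**Step 3: power by simulation.** Inputs from the SAP: 240 per arm, two-sided 0.05, and a logistic model with treatment, HD stage, neuroleptic use and region. Assumed: 35% responders on placebo and 48% on active; correlation ρ between own Baseline and latent change of 0 to 0.5 in absolute value; correlation r between Baseline UHDRS-TFC and own Baseline of 0.3 or 0.6; no missing data. There were 2,500 trials per setting, with both models fitted to each. Power (%), Baseline UHDRS-TFC / own Baseline:

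| ρ | r = 0.3 | r = 0.6 |
|---|---|---|
| 0 | 83.0 / 83.0 | 83.3 / 83.6 |
| 0.1 | 81.7 / 81.9 | 81.4 / 81.3 |
| 0.2 | 82.0 / 82.5 | 83.1 / 83.7 |
| 0.3 | 81.9 / 84.5 | 83.6 / 84.3 |
| 0.4 | 82.2 / 85.0 | 83.1 / 85.7 |
| 0.5 | 83.3 / 89.0 | 84.8 / 88.0 |

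The Monte Carlo error of one entry is about √(0.83 × 0.17 / 2500) = 0.75 points. Differences within a cell are more precise, because both models see the same trials.

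The gain does not come from a smaller standard error. At ρ = 0.5, r = 0.3 the mean log odds ratio moves from 0.559 to 0.655 and its standard error from 0.191 to 0.208. The ratio rises from 2.93 to 3.15.

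**Step 4: chance imbalance.** No true effect, r = 0.3, 1,500 trials per setting, own-Baseline imbalance fixed at 1.96 × √(2/240) = 0.179 SD:

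| ρ | log OR, UHDRS-TFC model | OR | log OR, own model | Rejection %, UHDRS-TFC / own |
|---|---|---|---|---|
| 0.1 | 0.028 | 1.03 | 0.001 | 4.6 / 4.6 |
| 0.2 | 0.054 | 1.06 | 0.000 | 5.5 / 4.9 |
| 0.3 | 0.086 | 1.09 | 0.004 | 6.8 / 5.5 |
| 0.5 | 0.138 | 1.15 | 0.002 | 10.1 / 5.1 |

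The standard error of the log odds ratio in the UHDRS-TFC model is about 0.194, so the shift is roughly 0.14 to 0.71 of it.

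**Step 5: type I error over all randomizations.** With 2,500 trials, rejection was 4.2% with either covariate at ρ = 0.2. At ρ = 0.5 it was 6.0% (UHDRS-TFC) and 5.4% (own). The Monte Carlo error is √(0.05 × 0.95 / 2500) = 0.44 points. The 6.0% is about 2.2 errors above 5%, but randomization gives no reason for a real excess.

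**Cross-check.** A large-sample simulation of a UHDRS-TMS-like score (correlation of true score with UHDRS-TFC −0.4, response defined as change ≤ 0) gave Wald chi-square ratios, own Baseline over Baseline UHDRS-TFC, of 1.001, 1.015, 1.045 and 1.071 at assumed test-retest reliabilities of 0.95, 0.90, 0.80 and 0.70. That is 0 to 7% more effective sample size, the same order of gain.

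**The case against.** The strongest reply is that SAP 7.5 says only that the analysis is similar. In the UHDRS-TFC model the Baseline term is the endpoint's own, so a similar model for UHDRS-TMS could mean Baseline UHDRS-TMS, in keeping with the continuous and NfL models. The sentence in 7.4.3 that appears to fix the model also cites a section without one. This stands in part: the carry-over is the literal reading, not an explicit instruction. It does not remove the point, because a programmer following the only covariate list would fit Baseline UHDRS-TFC, and a pre-specified model should not leave the choice open.

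Three further replies stand:
- Covariate wording for Q-Motor may lie under the redaction in 7.5, so nothing firm can be said there.
- cUHDRS contains UHDRS-TFC as one of four components (SAP 12.1.3), so Baseline UHDRS-TFC already corrects in part.
- The binary and continuous versions differ by design. SAP 7.1.1 gives responders a composite plus hypothetical strategy and changes from Baseline a treatment-policy strategy. A reader might infer that any disagreement between them comes from the covariate. The documents do not support that.

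A reader might also infer that the imputation model has the same gap. It does not: SAP 5.8.1.2 already includes the imputed endpoint's own Baseline.

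**Conclusion.** The point holds as a small, no-cost improvement to secondary analyses outside the testing hierarchy. It is firm for UHDRS-TMS and cUHDRS, and conditional for Q-Motor. Using the own Baseline would add about 0 to 6 points of power, and under 1 point for ρ up to 0.2. It would remove a log odds ratio shift of about 0.03 to 0.14 in a trial with a roughly 2-standard-error imbalance.

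These sizes depend on the responder rates and correlations assumed above. The simulation also gives Baseline UHDRS-TFC no predictive value beyond the own Baseline, which favours the change. HD stage, itself a grouping of UHDRS-TFC, stays in both models.

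Three stronger inferences should be resisted:
- **Lost precision in the odds ratio.** The standard error rises slightly with the own Baseline. The gain is in power.
- **Inflated type I error.** The excess rejections in Step 4 are conditional on an unlucky imbalance. Averaged over randomizations, the error stays near 5%.
- **A threat to confirmatory tests.** UHDRS-TFC response, second among the ranked secondary endpoints, already uses its own Baseline. The only other binary endpoint in the hierarchy, CGI-C at Week 65, is a change rating with no Baseline value.

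**What to change.** Add to SAP 7.5, and to 7.4.3 for consistency: *For responder endpoints derived from a variable with a Baseline value, the Baseline value of that variable replaces Baseline UHDRS-TFC in the logistic model.* With this wording CGI-C keeps Baseline UHDRS-TFC.

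Correct the cross-reference in 7.4.3 from Section 7.4.1 to 7.4.2. SAP 7.7 points to 7.4.1 for its logistic regression too and needs the same correction. The imputation model needs no change.

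The cost is one sentence and two section numbers. The Baselines are already collected and already used in the continuous models. The change belongs in an addendum before database lock and unblinding. After that, the own-Baseline fit should be reported as a change to the planned analyses.
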